First 36 subjects: PK blood samples in subjects < 10 kg at Baseline a,b	Predose, EOI, and 48-96 h	Predose	Predose and EOI	Predose	Predose and EOI	Predose	Predose	Predose and EOI	Predose	X	X
First 36 subjects: PK blood samples in subjects ≥ 10 kg at Baseline a,b	Predose, EOI, 3 h, and 48-96 h	Predose	Predose and EOI	Predose	Predose and EOI	Predose	Predose and EOI	Predose and EOI	Predose	X	X
PK blood samples in subjects beyond the first 36 a,b	Predose and EOI	Predose	Predose and EOI	Predose	Predose and EOI	Predose	Predose	Predose and EOI	Predose	X	X
Blood samples for ADA (immunogenicity) testing c	Predose	Predose	Predose	Predose	Predose	—	Predose	Predose	Predose	X	X

ADA: antidrug antibodies; EOI: end of infusion; EOT: End of Treatment; PK: pharmacokinetic(s).

- Predose blood samples for PK determinations will be collected from all subjects within 2 hours prior to trial treatment infusion. PK, ADA, and biomarker samples collected at the same predose time point can be used interchangeably if the dedicated sample has insufficient quantity, as the subject's parent(s)/guardian(s) will have consented to all collections and tests. PK sampling can be adjusted based on the PK data obtained from the first 3 subjects.
- Postdose samples for PK analysis will be collected at EOI and at the subsequent times indicated. The timepoint window for the EOI and 3-hour samples is ± 30 minutes. Additional PK samples will be collected during the EOT/Withdrawal Visit and at the 30-day Safety Follow-up Visit. PK samples for avelumab will be collected from all subjects in Phase I and Phase II of the study. Every effort should be made to collect PK samples as close to the protocol-prescribed time point as possible, and to record the exact time in source document. Protocol deviations will be captured if samples are not collected, or if sample collection times are not recorded.

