#### 5.1.1.1 Phase I Study Design

In the dose-finding part of the study, subjects will be enrolled in sequential cohorts of 3 to 6 subjects each; the first 3 subjects will be  $\geq 1$  year old. At least 12 subjects must be evaluable for the primary analysis. Phase I will be completed when at least 12 DLT-evaluable subjects have been treated at a dose level confirmed to be safe. Phase II will then begin.

The starting dose will be the same as recommended dose in adults, 10 mg/kg avelumab administered intravenously (iv) once every 2 weeks, which is based on modeling and simulation results using adult PK data from ongoing avelumab studies as described in Section 5.2. Avelumab will be administered until confirmed progression, death, unacceptable toxicity, or any criterion for withdrawal occurs. In Phase I, the DLT observation period is defined as a 28-day period (2 cycles) beginning with the first avelumab administration.

The first cohort of 3 to 6 subjects will be enrolled at the starting dose level of 10 mg/kg (DL1). Based on the number of subjects experiencing DLTs at the completion of the first cohort, the dose for the next cohort of subjects can be kept the same or modified.

- If DL1 is confirmed as safe, this dose will be selected as RP2D if it provides adequate exposure in children compared with adults.
- If exposure is not adequate (when compared with adult population PK [PopPK]-simulated values for median and distribution of exposure [ $C_{max}$ , AUC, and  $C_{trough}$ ]), a decision can be made to escalate to a dose level up to 20 mg/kg (DL2).
- If at any point the modified toxicity probability interval (mTPI) results indicate a dose de-escalation is warranted, the next subjects will be enrolled at lower dose level of 3 mg/kg every 2 weeks (DL -1). Dose re-escalation can be permitted based on the mTPI results as long as the current dose level has not been determined to have exceeded the MTD. The MTD estimate is the highest dose tested of avelumab associated with the occurrence of DLTs within the first 2 cycles of treatment in < 33% of subjects, provided that a higher dose level of avelumab was tested and had an associated DLT rate  $\geq$  33%.

Subjects will return to the clinic at regular intervals for assessments (see Section 7.1 and Table 1).

Avelumab treatment will continue until:

- PD (see Section 5.5.1) or death
- Unacceptable toxicity
- Any criterion for withdrawal from the trial or trial treatment is fulfilled (see Section 5.5).

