### **6.2 Dosage and Administration**

#### **6.2.1 Avelumab**

Subjects will receive an iv infusion of avelumab over 1 hour (-10 minutes/+20 minutes, ie, 50 to 80 minutes) once every 2 weeks.

The dose of avelumab will be calculated based on the weight of the subject determined within 72 hours prior to administration. The dose of avelumab used for the previous administration can be repeated if the change in the subject's weight is within 10% of the weight used for the last dose

calculation. Subjects will receive avelumab once every 2 weeks until the criteria in Sections 5.4, 5.5.1, and 5.5.2 are met.

Rules for dose modifications during the Phase I part of the study are described in Section 5.1.1.1. Modifications of the infusion rate due to infusion-related reactions are described in Section 6.5.5.1.

In order to mitigate infusion-related reactions, premedication with an antihistamine (H1 receptor blocker such as diphenhydramine) and with acetaminophen (paracetamol) approximately 30 to 60 minutes prior to each dose of study drug for the first 4 infusions is mandatory. This regimen may be modified based on local treatment standards and guidelines, as appropriate. Steroid premedication specifically for avelumab is not permitted.

Avelumab treatment may continue past the initial determination of confirmed progression per irRECIST as long as the following criteria are met:

- No new symptoms or worsening of previous symptoms
- Tolerance of avelumab
- Stable performance status (Lansky performance status  $\geq 50\%$  for subjects  $\leq 16$  years of age, or Karnofsky scale  $\geq 50\%$  for subjects  $> 16$  years of age)
- Treatment will not delay an imminent intervention to prevent serious complications of disease progression (eg, CNS metastases)

The decision to continue treatment should be discussed with the Medical Monitor and documented in the trial records.

A radiographic assessment should be performed within 8 weeks of original PD to determine whether there has been a decrease in the tumor size, or confirmed PD per irRECIST. The assessment of clinical benefit should be balanced by clinical judgment as to whether the subject is clinically deteriorating and unlikely to receive any benefit from continued treatment with avelumab.

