**Table 4 Treatment Modification for Symptoms of Infusion-related Reactions Associated with Avelumab**

NCI-CTCAE Grade	Treatment Modification for Avelumab

Grade 1 – mild
 
 
• Mild transient reaction; infusion interruption not indicated; intervention not indicated.
 
	
 
• Decrease the avelumab infusion rate by 50% and monitor closely for any worsening.
 

Grade 2 – moderate
 
 
• Therapy or infusion interruption indicated but responds promptly to symptomatic treatment (eg, antihistamines, NSAIDs, narcotics, iv fluids); prophylactic medications indicated for ≤ 24 hours.
 
	
 
• Temporarily discontinue avelumab infusion.
 
• Resume infusion at 50% of previous rate once infusion-related reaction has resolved or decreased to at least Grade 1 in severity, and monitor closely for any worsening. Infusion time should be extended to 2 hours, and subject should receive the full dose.
 

Grade 3 or Grade 4 – severe or life-threatening
 
 
• Grade 3: Prolonged (eg, not rapidly responsive to symptomatic medication and/or brief interruption of infusion); recurrence of symptoms following initial improvement; hospitalization indicated for clinical sequelae.
 
• Grade 4: Life-threatening consequences; urgent intervention indicated.
 
	
 
• Stop the avelumab infusion immediately and disconnect infusion tubing from the subject.
 
• Subjects have to be withdrawn immediately from avelumab treatment and must not receive any further avelumab treatment.
 

iv: intravenous; NCI-CTCAE: National Cancer Institute-Common Terminology Criteria for Adverse Event; NSAIDs: nonsteroidal anti-inflammatory drugs.

Once the avelumab infusion rate has been decreased by 50% or interrupted due to an infusion-related reaction, it must remain decreased for all subsequent infusions. If a subject experiences a Grade 3 or Grade 4 infusion-related reaction at any time, the subject must discontinue avelumab. If an infusion reaction occurs, all details about drug preparation and infusion must be recorded.

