16.1.1 PK Concentration Data

Pre-dose samples that occur before the first drug administration will be assigned a time of 0 hours, as if the sample had been taken simultaneously with the study drug administration.

Values below the lower limit of quantification of the assay (LLOQ) will be taken as zero for summary statistics of PK concentration data. Missing concentrations (e.g. no sample, insufficient sample volume for analysis, no result or result not valid) will be reported and used generally as "N.R."

PK concentrations which are questionable due to a protocol deviation (as defined in the CTP), documented handling error or analytical error (as documented in the bioanalytical report) may be excluded from the PK analysis if agreed upon prior to performing a statistical analyses. In this case the rationale for exclusion must be provided in the Clinical Study Report (CSR). Any other PK concentrations that appear implausible to the Pharmacokineticist/PKPD Data Analyst must not be excluded from the analysis. Any implausible data will be documented in the Clinical Study Report (CSR).

Based on Table 2 (Schedule of Assessments – Pharmacokinetic and Antidrug Antibody Sampling) of the CSP, the timepoint window for the EOI and 3-hour samples is ± 30 minutes. Samples that are collected outside the specified time windows will be included in the PK parameter estimation (NCA) but will be excluded from the concentration summary and mean concentration plots.

Serum avelumab PK concentration data will be listed and summarized by dose level, day and nominal time using standard descriptive statistics including the number of non-missing observations (N), arithmetic mean (Mean), standard deviation (SD), coefficient of variation (CV%), minimum (Min), median (Median), and maximum (Max).

Individual concentration-time profiles showing all subjects by dose level will be created using the actual time points and the numeric concentration data. Arithmetic mean concentration-time profiles by dose level/cohort will be provided using scheduled (nominal) time points and the numeric concentration data. All concentration-time plots for PK data will be presented both on a linear and on a semi-logarithmic scale. Mean plots will include SD error bars when plotted on a linear scale.

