AUC_{τ}/Dose	The Dose normalized AUC over the interval from $T_1=0$ h to $T_2=336$ h. Normalized using actual dose, using the formula AUC_{τ}/Dose . This parameter is calculated following dosing in Cycle 1, Day 1 only. Unit = $\mu\text{g}\cdot\text{h}/\text{mL}/\text{mg}$.
AUC_{0-t}	The area under the concentration-time curve (AUC) from time zero (= dosing time) to the last sampling time (t_{last}) at which the concentration is at or above the lower limit of quantification. Calculated using the mixed log linear trapezoidal rule (linear up, log down). This parameter is calculated following dosing in Cycle 1, Day 1 only. Unit = $\mu\text{g}\cdot\text{h}/\text{mL}$.

Symbol	Definition
$AUC_{0-t}/Dose$	The Dose normalized AUC from time zero to the last sampling time (t_{last}) at which the concentration is at or above the lower limit of quantification. Normalized using the actual dose, using the formula $AUC_{0-t}/Dose$. This parameter is calculated following dosing in Cycle 1, Day 1 only. Unit = $\mu\text{g}\cdot\text{h}/\text{mL}/\text{mg}$.
$AUC_{0-\infty}$	The AUC from time zero (dosing time) extrapolated to infinity, based on the predicted value for the concentration at t_{last} , as estimated using the linear regression from λ_z determination. $AUC_{0-\infty}=AUC_{0-t}+C_{last\ pred}/\lambda_z$ This parameter is calculated following dosing in Cycle 1, Day 1 only. Unit = $\mu\text{g}\cdot\text{h}/\text{mL}$.
$AUC_{0-\infty}/Dose$	The Dose normalized AUC from time zero extrapolated to infinity. Normalised using actual dose, using the formula $AUC_{0-\infty}/Dose$. This parameter is calculated following dosing in Cycle 1, Day 1 only. Unit = $\mu\text{g}\cdot\text{h}/\text{mL}/\text{mg}$.
$AUC_{extra\%}$	The AUC from time t_{last} extrapolated to infinity given as percentage of $AUC_{0-\infty}$. $AUC_{extra} = (\text{extrapolated area}/AUC_{0-\infty})*100$. This parameter is calculated following dosing in Cycle 1, Day 1 only. Unit = %.
C_{EOI}	Concentration at the end of infusion. Unit = $\mu\text{g}/\text{mL}$.
CL	The total body clearance of drug following intravenous administration. $CL = Dose_{i.v.}/AUC_{0-\infty}$. This parameter is calculated following dosing in Cycle 1, Day 1 only. Unit = L/h.
C_{max}	Maximum observed concentration. This parameter is calculated following dosing in Cycle 1, Day 1 only. Unit = $\mu\text{g}/\text{mL}$.

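### The symmetric ±30-minute window for the end-of-infusion sample reaches back into the infusion, so an in-window C_EOI can be far too low at any weight; Cycle 1 Cmax and AUC are materially affected only below 10 kg

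*Protocol*

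**What the plan says.** - **Infusion length.** Protocol 6.2.1: "Subjects will receive an iv infusion of avelumab over 1 hour (-10 minutes/+20 minutes, ie, 50 to 80 minutes) once every 2 weeks". After a Grade 2 infusion-related reaction, Protocol Table 4 adds: "Infusion time should be extended to 2 hours".
- **Sampling window.** Protocol Table 2, second footnote: "The timepoint window for the EOI and 3-hour samples is ± 30 minutes". The same footnote introduces these draws with "Postdose samples for PK analysis will be collected at EOI and at the subsequent times indicated". It asks sites to sample as near the set time as they can and to record the exact time. The only PK sampling failures it names as deviations are a missed sample and an unrecorded time.
- **Cycle 1 schedule, first 36 subjects (Table 2).** Below 10 kg: "Predose, EOI, and 48-96 h". From 10 kg upwards there is also a 3-hour sample. Phase I plans 12 to 36 subjects, so this schedule covers it.
- **SAP handling.** SAP 16.1.1 adopts the same window. Out-of-window samples stay in the non-compartmental analysis but "will be excluded from the concentration summary and mean concentration plots". Values that merely look implausible may not be dropped.
- **SAP parameters.** SAP 16.1.2 defines C_EOI as "Concentration at the end of infusion" and Cmax as the highest observed value in Cycle 1. Neither definition corrects for a draw made during the infusion. AUC uses actual elapsed times.
- **Use.** Protocol 5.1.1.1 judges whether exposure at the starting dose is adequate by comparing Cmax, AUC and Ctrough with adult simulated values. SAP 16.1.2.2 summarises C_EOI, Ctrough and single-dose parameters by weight, split at 10 kg.

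**The concern.** A symmetric window suits a sample on a slowly falling curve. The end-of-infusion sample sits at a sharp corner. Before it the concentration climbs in step with the dose delivered, and after it the concentration barely moves for half an hour. The minus side of the window therefore admits samples that are not post-dose at all, contrary to the footnote's own description. Nothing in either document catches them: such a draw is in window, is not a named deviation, and may not be excluded as implausible.

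The error goes one way, towards apparent under-exposure. It enters every C_EOI summary directly. It reaches Cmax and AUC only where no other sample was taken soon after the infusion. In Cycle 1 of Phase I that means the subjects under 10 kg. Because the single-dose summaries are split at 10 kg, early draws could also create an artificial difference between the two weight groups.

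**Working it through.** **Inputs.** Infusion length T is 50, 60 or 80 minutes (Protocol 6.2.1), or 120 minutes (Table 4). The window edge is -30 minutes (Table 2). The documents give no half-life, so a one-compartment model with a half-life of 3 to 8 days is assumed.

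**Step 1: the plan's own range.** 60 - 10 = 50 and 60 + 20 = 80 minutes, as stated.

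**Step 2: share of dose given 30 minutes before the end**, at a constant rate, = (T - 30)/T.

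| T (min) | Share of dose in |
|---|---|
| 50 | 20/50 = 40% |
| 60 | 30/60 = 50% |
| 80 | 50/80 = 62.5% |
| 120 | 90/120 = 75% |

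Elimination over 30 minutes is negligible, so C_EOI reads at about these percentages of its true value. This step needs no half-life. The mean C_EOI depends on how often early draws occur: with a 60-minute infusion, if a quarter of subjects were drawn at the edge, it would be 1 - 0.25 × 0.5 = 87.5% of true.

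**Step 3: Cmax below 10 kg, 60-minute infusion.** The observed Cmax is the larger of the early draw (50%) and the 48-96 h sample. The latter, relative to the true peak, is 2^(-(t - 1)/half-life):
- 3 days, 96 h: 2^(-95/72) = 40%, so Cmax is the early draw, 50%.
- 3 days, 48 h: 2^(-47/72) = 64%.
- 8 days, 96 h: 2^(-95/192) = 71%.
- 8 days, 48 h: 2^(-47/192) = 84%.

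The range is 50% to 84%.

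**Step 4: AUC(0-336 h) below 10 kg**, by the linear-up/log-down rule, with the Cycle 2 predose sample as the 336-h point and concentrations in units of dose/volume. For a 3-day half-life and a 96-h sample, the concentrations are 0.499 (early draw) or 0.995 (true end), then 0.399 at 96 h and 0.040 at 336 h.
- Early: 0.1 + 95.5 × (0.499 - 0.399)/ln(0.499/0.399) + 37.3 = 0.1 + 42.7 + 37.3 = 80.1.
- Correct: 0.5 + 95 × (0.995 - 0.399)/ln(0.995/0.399) + 37.3 = 0.5 + 62.0 + 37.3 = 99.8.
- Ratio: 80.1/99.8 = 80%.

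For an 8-day half-life and a 48-h sample the ratio is 182.8/194.5 = 94%. The other two combinations give 88% and 89%.

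**Step 5: from 10 kg upwards.** The 3-hour sample replaces the early draw as the maximum. Taken 3 hours after the end of infusion, it reads 2^(-3/72) = 97% to 2^(-3/192) = 99% of the peak. Counted from the start it reads 98% to 99%. AUC is at least 99% either way.

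**Step 6: sensitivity.**
- Half-life 2 to 10 days, below 10 kg: Cmax 50% to 87%, AUC 75% to 95%. A 50-minute infusion takes the worst Cmax to 40%.
- Fast initial distribution (40% with a 12-hour half-life, 60% with 96 or 144 hours): below 10 kg, Cmax is 50% to 51% and AUC 80% to 91%; from 10 kg, Cmax is about 95% and AUC at least 99%.

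**Step 7: the plus side.** A draw 30 minutes after the end reads 99.5% (3 days) to 99.8% (8 days) of the peak, so that half of the window does no harm.

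**The case against.** A reader might infer that the window distorts the choice of the recommended Phase II dose in general. The documents do not support that.
- C_EOI is not among the three measures compared with adults, and Ctrough is unaffected.
- In Phase I every subject of 10 kg or more should have a 3-hour sample in Cycle 1, which almost removes the effect on Cmax and AUC.
- The early look at 3 subjects is restricted to children aged at least 1 year. Nothing shows that any of them would weigh under 10 kg.
- The comparison uses the median and distribution, and a median resists isolated early draws.
- Going above the starting dose also requires that dose to have been shown safe, and the Safety Monitoring Committee decides.

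These points stand. So does the point that the figures describe the edge of the window. Sites are told to sample close to time, and the documents do not show how often early draws occur. A population PK model using actual times can allow for a mid-infusion draw.

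The objection does not remove the defect. Encouraging punctuality does not change what counts as valid. Actual times do not repair an observed C_EOI or Cmax, and they do not restore the AUC missed by a trapezoid drawn from a mid-infusion point. After Cycle 1, the end-of-infusion draw is the only sample taken soon after the infusion during treatment, at any weight.

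**Conclusion.** The window is wrongly specified and should be corrected. An in-window C_EOI can read at 40% to 62.5% of true for the standard infusion range, at any weight and in any cycle with an end-of-infusion draw. That result rests only on a constant infusion rate.

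For the Phase I exposure comparison the effect is material only below 10 kg and at the window's edge. With a 60-minute infusion and an assumed half-life of 3 to 8 days, Cycle 1 Cmax reads about 50% to 84% and AUC(0-336 h) about 80% to 94% of the correctly timed value. From 10 kg upwards the loss is about 1% to 3% in Cmax (about 5% if initial distribution is fast) and under 1% in AUC. This is a matter of sound PK reporting, particularly in the smallest children. It is not evidence that the dose decision was biased.

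Subjects beyond the first 36 have only predose and end-of-infusion draws in Cycle 1, so their Cmax would equal C_EOI. They come after the Phase I decision, and the SAP modification history says monotherapy evaluation ended after Phase I.

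**What to change.** **Protocol Table 2 and SAP 16.1.1.** Set the end-of-infusion window at 0 to +30 minutes after the actual end of infusion. Keep ±30 minutes for the 3-hour sample.

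**SAP rule for samples already taken.** With Phase I over, this is the part that matters most.
- Treat an end-of-infusion sample timed before the recorded end of infusion as out of window, flag it, and omit it from C_EOI summaries and plots.
- If the subject has no other sample within hours after the infusion, set Cycle 1 Cmax to missing. Merely barring the early draw would pass the 48-96 h value off as Cmax, at 40% to 84% of true in the model above.
- In the same subjects, flag AUC and the parameters derived from it, and leave them out of the summary statistics or show the summaries with and without them. Relabelling the sample is not enough, because SAP 16.1.1 keeps out-of-window samples in the non-compartmental analysis and the AUC shortfall would remain.

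**Cost.** One line in the protocol table and one SAP rule. Sample times are already required; the rule also needs the recorded infusion stop time. A few C_EOI, Cmax or AUC values would drop out of the summaries, which matters most in the under-10 kg group if it is small.

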## 2 Sponsor, Investigators, and Trial Administrative Structure

The Sponsor of this clinical trial with avelumab is EMD Serono Research & Development Institute, Inc. (EMD Serono R&D), Billerica, MA, in the United States of America (USA), and Merck KGaA, Darmstadt, Germany, outside the USA.

A contract research organization (CRO), PPD [REDACTED] will undertake the operational aspects of this study. Details of such structures and associated procedures will be defined in a separate Integrated Project Management Plan maintained by QuintilesIMS. The Integrated Project Management Plan will be prepared by the QuintilesIMS Clinical Project Manager in cooperation with other QuintilesIMS Operational Team Leads.

The Coordinating Investigator, PPD [REDACTED], represents all Investigators for decisions and discussions regarding this trial, consistent with the International Council for Harmonisation (ICH) Topic E6 Good Clinical Practice (GCP; hereafter referred to as ICH GCP). The Coordinating Investigator will provide expert medical input and advice relating to trial design and execution and is responsible for the review and signoff of the clinical trial report.

Signature pages for the Protocol Lead and the Coordinating Investigator as well as a list of Sponsor responsible persons are in [Appendices](#).

The trial will appear in the following clinical trial registries: EU Clinical Trials Register, <https://www.clinicaltrialsregister.eu/> (registration number 2017-002985-28) and ClinicalTrials.gov (USA), <https://clinicaltrials.gov/> (registration number to come).

